## 8) DATA COLLECTION AND CONFIDENTIALITY

#### 8.1 Data Collection

Data collection will take place in line with the aforementioned procedures. Interview data will be collected via one-to-one interviews at baseline and end-of-study. Quantitative outcomes will be collected via Qualtrics at baseline, 4-weeks, 12-weeks and end-of-study. Feasibility data will be recorded by the researcher during each peer support group.

# 8.2 Confidentiality

The following steps will be taken to ensure confidentiality during the course of the study:

- 1) All participants will be assigned a participant number. Questionnaire data will only be linked to a participant via participant number. Participants will be sent an email with their participant ID prior to them completing each questionnaire and they will be asked to input this ID on the questionnaire. Participant names and other identifying information will be removed from all transcripts. A pseudonymisation key will be stored electronically and separately from all research data (the pseudonymisation key will be stored on the P: Drive and all research data will be stored on the Research Data Management System (RDMS)). The pseudonymisation key will be permanently deleted following completion of all study procedures and data analysis, at which point the dataset will be fully anonymised.
- 2) Interview transcripts will be pseudonymised by removing any information that could identify the participant and replacing it with a generic description (e.g., 'Manchester' would be changed to '[name of city]'). This will be done for all information that could contribute to the identification of the participant or other.
- 3) Data containing personal information will be stored separately from pseudonymised research data. Personal information will be stored on the University's P: Drive, and all research data will be stored on the RDMB.
- 4) Interview data will be transferred immediately from the recording device (including Zoom/MS Teams server) to the RDMS. The recording will then be permanently deleted from the recording device.

- 5) Interviews will be transcribed primarily by the researcher (AB). However, where third parties are required to assist with transcription, they will:
  - a. Be students from the University of Manchester, meaning data will not have to be moved/shared from the University's secure network.
  - b. Sign a strict confidentiality agreement (found at Appendix B of University Standard Operating Procedures document titled: taking recording of participants for research projects).
  - c. Have access to recordings only (not consent forms, demographic information, or questionnaires).
  - d. Complete transcription on University property or in their private residence using a University laptop connected to the University's secure VPN. As such, the audio recordings and transcripts will not have to be transferred/shared from the University's secure network.
- 6) Recordings of interviews will be permanently deleted from the University server as soon as possible following transcription.
- 7) Where participants indicated they would like to receive information about study findings, be invited to take part in member checking, or receive information about future studies, a record will be made and stored separately and securely on the P: Drive, separate from the research data.
- 7) The limits of confidentiality will be outlined on the PIS. Confidentiality will only be broken if there is a risk of harm to the participant or other. In such an event, the researcher will inform the supervisory team at the earliest opportunity. Where appropriate, the participant will be informed that confidentiality will need to be broken. However, where informing a participant would increase risk or jeopardise a potential safeguarding investigation, they will not be informed.
- 8) At the beginning of each online peer support group meeting, it will be reiterated that all personal information shared within the group is to be kept confidential.

Participants will be advised that they do not need to share their full name or contact information with other participants, and that they should only share what they are comfortable with within the group.

- 9) Ineligible participants will have their telephone screening proforma deleted immediately and permanently. These participants will be counted for CONSORT reporting purposes, but no personal data will be retained.
- 10) Consent forms and participant data will be retained in line with the University of Manchester's Records Retention schedule. Following the minimum retention period of five years, all research data will be permanently deleted from University servers. After a minimum retention period of seven years, all consent forms will be deleted from University servers.
- 11) Where participants request compensation via shopping voucher, the participant's name and email address will be passed along to the University of Manchester's Finance Department (as outlined in the PIS and CF). This is to enable the Finance Department to send the voucher to the participant electronically. The data will be retained for a minimum period of seven years, in line with the Records Retention Schedule.

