# Participant Risk of Harm to Self/Others

During the course of the research, a participant may disclose information that would indicate that they are at risk of harm to themselves/others. In this instance, the participant will be informed that the researcher or clinically-qualified co-facilitator (in cases where risk is disclosed during the hearing voices group) will need to break confidentiality and report

the risk, in the first instance, to the supervisory team. Information about breaking confidentiality is outlined in the PIS and CG and will be reiterated before each assessment and peer support group meeting.

To further mitigate participant risk of harm, the following procedure will be adhered to. Prior to commencing any study procedures, AB will collect the name and contact information of the care coordinator for those recruited from NHS trusts, and the name and contact information of the GP of participants recruited from voluntary/third-sector organisations and social media. AB will also collect the postcodes of all participants to ensure that emergency services are able to locate the participant quickly should an emergency arise.

All assessments and groups will take place online via videoconference. Participants will be advised that they can turn their camera off if they feel more comfortable doing so.

Prior to any interview or assessment, the following steps will be taken:

- 1) AB will familiarise herself with local support services/safeguarding teams and ensure that she has the contact information for the participant's care coordinator (for those recruited from NHS Trusts) or GP (for those recruited from voluntary/third-sector organisations or via social media).
- 2) AB will inform her supervisory team of the time and place of the assessment. This is to ensure that there is clinical cover at the time of the assessment and that the location is known. If no member of the supervisory team is available, another clinically trained researcher in the Division of Psychology and Mental Health will provide clinical cover.
- 3) AB will remind the participant that the assessment will be audio recorded.
- 4) AB will explain that all information disclosed during the course of the assessment will be kept confidential, except in cases where there is immediate risk of harm to the participant or others. In this instance, AB will inform her supervisory team and the care coordinator or GP of the participant.

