Data will be stored in accordance with the General Data Protection Regulation (GDPR) and the Data Protection Act of 2018. Participants' confidentiality will be maintained by removing any identifying information from research material (e.g., names, locations) and assigning each participant a unique participant ID (i.e., P01, P02) which will be used throughout the study. Participant data will be stored on the UoM's secure RDMS. A participant ID key will be stored on the UoM P: Drive; a separate, secure system from the RDMS which enables identifiable information to be stored separately from all other participant data. The pseudonymisation key will be destroyed following completion of all study procedures and data analysis, at which point the data will be fully anonymised.

The only instance in which confidentiality will be broken is if there is a risk of harm to the participant or others. The participant will be informed of this on the PIS and CF and it will be reiterated by AB at the beginning of each assessment and group meeting. In such an instance, AB will inform the participant that confidentiality will need to be broken and then will notify the supervisory team at the earliest opportunity and follow the safeguarding and reporting guidelines in the Safeguarding Protocol.

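### Section 13.2 tells staff to inform the participant before breaking confidentiality without the exception in section 8.2, and its pre-assessment script gives a narrower limit than the rule applied elsewhere

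*Protocol*

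**What the plan says.** Protocol section 8.2 sets the limit of confidentiality as follows: "Confidentiality will only be broken if there is a risk of harm to the participant or other". It has the researcher tell the supervisory team promptly and makes telling the participant conditional on its being appropriate. It then adds a prohibition: "where informing a participant would increase risk or jeopardise a potential safeguarding investigation, they will not be informed". It does not say whether the team or the participant is told first.

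Section 13.2 returns to the subject in two subsections.

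- *Participant Risk of Harm to Self/Others* opens with the case of a participant whose disclosure indicates a risk of harm and continues: "In this instance, the participant will be informed that the researcher or clinically-qualified co-facilitator" will have to break confidentiality and report to the supervisory team. Further down is a list introduced by "Prior to any interview or assessment, the following steps will be taken". In step 4 of that list the researcher explains that what is said stays confidential, "except in cases where there is immediate risk of harm to the participant or others".
- *Data Protection and Confidentiality* states: "The only instance in which confidentiality will be broken is if there is a risk of harm to the participant or others". It says the information sheet and consent form carry this limit and that "it will be reiterated by AB at the beginning of each assessment and group meeting". If the limit is reached, the researcher "will inform the participant that confidentiality will need to be broken and then will notify the supervisory team at the earliest opportunity", and then follows the Safeguarding Protocol.

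**The concern.** There are two separate inconsistencies.

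The first concerns what staff do. Section 8.2 recognises that telling a participant can itself be dangerous or can compromise an investigation, and it forbids telling them in that case. Section 13.2, where a researcher would look when a risk is disclosed, directs that they be told and gives no sign that an exception exists. Someone working from 13.2 alone would take the step that 8.2 forbids, in the one situation where it does harm.

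The second concerns what participants are told. Before an interview on sensitive material they would hear that only an immediate risk will be passed on, while the rule applied is broader. A participant who disclosed a real but non-immediate risk would have it reported after being assured it would stay confidential. That bears on participant safety and honest consent, not on the analysis.

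**Working it through.** The protocol gives no figure to reproduce here. The check is a comparison of every statement on the point.

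| Place in protocol | Limit of confidentiality | Is the participant told that it will be broken? |
|---|---|---|
| 8.2 | Risk of harm | Where appropriate; forbidden if telling would raise the risk or harm an investigation |
| 13.2, Risk of Harm, opening | Risk of harm | Yes, no condition |
| 13.2, Risk of Harm, step 4 | Immediate risk of harm | Not addressed; this is the advance explanation |
| 13.2, Data Protection | Risk of harm | Yes, no condition, and placed before notifying the team |

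**Informing the participant.** Three statements govern this, and the exception is in 1 of them. Take a disclosure where telling the participant would increase the risk. Under 8.2 they must not be told. Under either 13.2 statement they are told. No action satisfies both.

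**Order.** Section 8.2 fixes no order, so the order as such is not contradicted. But the Data Protection subsection links the two acts with *and then*. Followed literally in the excepted case, the forbidden step comes before the supervisory team has heard of the matter and could advise against it.

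**Threshold.** Three statements use risk of harm and one uses immediate risk of harm. The conflict falls in a single conversation: step 4 applies before every interview or assessment, and the Data Protection subsection says the broader limit is repeated at the start of each assessment. For a non-immediate risk disclosed at interview:

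- under step 4 it stays confidential;
- under 8.2 and the Data Protection subsection it is reportable.

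The word is not obviously idle. Section 6.2 excludes people at immediate risk of harm to themselves or others. If that criterion works, a risk disclosed by someone already enrolled may well be of the non-immediate kind.

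**How often step 4 is used.** There are two interview assessments per participant (baseline and end of study) and a target of 6 to 10 participants.

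- Lower end: 2 × 6 = 12 explanations.
- Upper end: 2 × 10 = 20 explanations.
- Group sessions affected by the step 4 wording: 0 of 26, because the list covers interviews and assessments only.

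These counts assume that everyone completes both assessments. They count how often the narrower wording would be spoken, not how often it would matter.

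**The case against.** The strongest reply is that 8.2 states a specific exception and 13.2 restates only the general rule. Nothing in 13.2 says *always*, the same researcher is bound by both sections, and a short restatement does not cancel an exception given elsewhere. In addition, the Data Protection sentence ends by sending the researcher to the Safeguarding Protocol, which is not shown and may contain the exception. On order, the same sentence asks for the team to be notified as early as possible, and the Risk of Harm subsection makes the team the first recipient of the report, so informing the participant is nowhere expressly made a precondition. On the threshold, *immediate* is one word against three consistent statements. The broader limit is also given in writing and repeated at the same assessments, and section 6.2 neither defines immediate risk nor ties it to confidentiality.

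Much of this lowers the practical risk. A careful reader of the whole protocol would probably apply the exception, clinical cover is arranged for assessments, and a clinically qualified co-facilitator is present in the groups. The ordering point is the weakest part and would not stand alone, and section 6.2 is only supporting evidence.

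The reply does not remove the conflict. The 13.2 text reads as a complete instruction and does not point to 8.2. An unseen document cannot reconcile two statements in this one. Repeating the broader limit at the assessment where step 4 gives the narrower one means participants hear two different limits.

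**Conclusion.** The concern holds on both counts. Section 13.2 twice directs an act that section 8.2 forbids in a defined situation, and step 4 describes a narrower limit than the one that will be applied. In size, the exception is missing from 2 of the 3 statements about informing, and the narrower limit would be given at 12 to 20 assessments if all participants complete both. The protocol gives no basis for estimating how often either conflict would arise, and in a study of 6 to 10 people it may never do so. The conclusion rests on the protocol text alone; the Safeguarding Protocol, information sheet and consent form could not be checked. Objectives, outcomes, sample size and analysis are untouched. The point should be corrected because it governs what staff do and what participants are promised when someone may be at risk.

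**What to change.** Use the rule in 8.2 throughout, with edits to three statements in section 13.2:

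1. In the opening of *Participant Risk of Harm to Self/Others*, say that the participant is informed where appropriate, but not where this would increase risk or compromise a safeguarding investigation.
2. In *Data Protection and Confidentiality*, add the same condition and replace *and then*, so that the supervisory team is notified promptly whether or not the participant has been told.
3. In step 4 of the pre-assessment list, delete *immediate*.

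Then confirm that the participant information sheet, the consent form and the Safeguarding Protocol state the same limit and the same exception. The cost is these wording edits and a check of three documents. No extra data, visits or staff are needed.

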#### 9) STATISTICAL CONSIDERATIONS

## 9.1 Statistical Analysis

Appropriate descriptive statistics (e.g., mean and standard deviation for continuous data; counts and percentages for categorical data) will be used to summarise: 1) feasibility measures in line with the CONSORT recommendations outlined above; 2) completeness of outcome measures; and 3) reason for withdrawal.

Linear regression models will be fit for each outcome measure with baseline measures of the outcome as fixed effects and the participant and group (in the event of multiple groups) as random effects.

In instances where a participant has completed a questionnaire, but not completed all questions within the questionnaire, the instrument-specific established procedures for

handling partially-missing data will be adhered to. When data are completely missing for a whole questionnaire, this will be noted.

#### 9.2 Qualitative Analysis

Participant interviews will be transcribed verbatim by AB or a member of the research team as soon as possible after the interview. To ensure confidentiality, all personal or identifiable information will be pseudonymised during the transcription process, and each participant will be given a unique pseudonym. Following transcription, audio recordings will be destroyed.

In order to answer questions about acceptability, the interviews will be analysed using Framework analysis, a commonly-used and suitable method of analysis for acceptability studies within applied health and social care research (Spencer et al., 2003). The purpose of Framework analysis is to answer discrete questions about acceptability by generating descriptions and explanatory conclusions clustered around themes. Framework analysis enables both theme-based and case-based analysis through the development of matrix tables that can be read across (cases) or down (themes) (Ward et al., 2013). Framework analysis adopts an ontological realist and an epistemologically flexible approach to research, and should be understood as a method of data analysis, as opposed to a research paradigm (Ritchie et al., 2003). Framework analysis possesses both the methodological rigour and transparency necessary for acceptability studies within health and social care, while maintaining the flexibility that is the hallmark of qualitative research (Swallow et al., 2011).

Data will be analysed using the following method. First, a process of data familiarisation will be undertaken, in which transcripts will be read and any early themes will be noted. This process sensitises the researcher to identify the within- and between-participant differences (Iliffe et al., 2015). Next, a thematic framework will be identified by identifying the key codes that exist within the transcripts (Iliffe et al., 2015). Transcripts will then be indexed by numerically annotating the data to find commonalities and consistencies (Iliffe et al., 2015). Data will then be charted in order to synthesize the codes and develop a final

coding framework (Iliffe et al., 2015). Finally, themes will be mapped graphically on to a matrix and interpreted in light of the research question (Iliffe et al., 2015).

Framework analysis theory emphasizes the researcher's active role in data generation and knowledge production and codes are representations of the researcher's interpretation of patterns of meaning across the dataset (Byrne, 2021). Accordingly, no two researchers would be expected to generate the same codes. As such, in this study, consensus among multiple coders will not be sought. However, in order both to sense-check and explore multiple assumptions and interpretations of the data (Byrne, 2021), codes and subsequent themes will be discussed with the supervisory team and PPIE experts.

## 9.3 Sample Size

A sample of between 6-10 participants will be both sufficient and manageable given the limited resources of this study. Preliminary evidence arising from qualitative interviews with group facilitators in Study 1 of this PhD, as well as feedback from PPIE experts, indicate that a minimum of 6 participants are needed to ensure sufficient diversity of participant experiences and to enable adequate flow of dialogue within the group. The group will be capped at 10 participants as group facilitators have noted that having groups with more than 12 participants total (including facilitators) becomes unmanageable online and can inhibit the flow of dialogue. 6-10 participants will also enable saturation of qualitative data (see below for an outline of the qualitative analysis). As this is a feasibility study, the study is not powered to detect effects in quantitative measures between baseline and end-of-study.

# 9.4 Member Checking

To enhance the validity and rigour of the data, the findings will subject to member checking by the study participants. Once the data have been analysed and preliminary themes and sub-themes have been generated, all participants who consented to member checking will be send a copy of the themes to verify that their experience maps onto the themes. Participants will be advised that the themes are meant to broadly capture all the different experiences endorsed, so their personal experiences may not align completely with each theme or sub-theme. Participants will be asked to provide either written or verbal feedback

on the clarity of the themes and accuracy of the interpretation. Specifically, participants will be asked if their experiences are fully captured by the themes and sub-themes, if they themes are sufficiently relevant and necessary to include, and if the interpretations are fair and representative (Creswell, 2005).

#### **9.5 PPIE Consultation**

At their core, HVGs are survivor-led initiatives; as such, it is imperative that various stakeholders have input at all stages of study design and delivery. Given the historic tension between the HVM and research bodies, AB has sought informal PPIE input from current members of the English HVN, including HVM leaders/trainers, group facilitators, activists and HVG participants. The consensus has been that given the structure of mental health care in the UK, it would be beneficial to establish a stronger evidence base for HVGs to enable them to be incorporated into NHS settings in the future, thus making them more widely available to voice hearers. These consultants have emphasised the importance fully maintaining HVM values within the constraints of research regulation.

Ongoing input will be sought from the Psychosis Research Unit and Complex Trauma and Resilience Research Unit PPIE advisory groups during the delivery of this study. Specifically, they have advised on the most appropriate inclusion criteria for this study, and provided feedback on the PIS, quantitative measures, and topic guides. Based on their recommendations, the topic guides have been amended to ask about adverse life events. Ongoing input will be sought on the interpretation and dissemination of study result

